- **Visit 3:** Day 57 ± 4 (1st Treatment completion)
- **Visit 4:** Day 141 ± 7 (Interim)
- **Visit 5:** Day 281 ± 14 (2nd Treatment start)
- **Visit 6:** Day 337 ± 14 (2nd Treatment completion)
- **Visit 7:** Day 365 ± 14 (4 weeks post – treatment)

The primary efficacy endpoint is the proportion of patients in each treatment group with a complete therapeutic cure of onychomycosis of the target toenail assessed at Day 141 and at the last test-of-cure visit at Day 365 following either one 8-week treatment period or two 8-week treatment periods. The safety profile of each treatment group will be evaluated by comparing adverse events, application site reactions, monitoring vital signs and changes in clinical laboratory results obtained throughout the study.

The definitions of efficacy variables are stated below:

- **Complete Therapeutic cure:** Complete Clinical Cure **and** Mycological Cure
- **Complete Clinical Cure:** A patient with 0% nail involvement
- **Mycological Cure:** Negative KOH **and** negative culture for dermatophytes associated with onychomycosis
- **Satisfactory Clinical Cure:** ≤ 5% of the target toenail involvement

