9.6.13 Visual Assessment and Planimetry

At screening, both big toenails can be evaluated for nail involvement if the subject has a bilateral infection of the big toenails. At Visit 2, the target toenail will be identified and nail involvement of the target toenail over time will be monitored visually by an investigator at every visit. If the nail involvement does not reach zero at the final visit, the investigator will visually assess the nail involvement based on the following range:

- 0%
- > 0-5%
- 6-9%
- 10-35%
- > 35%

At Visit 2 and all subsequent visits, the target toenail will also be monitored by planimetry. Appropriate photographic documentation of the target toenail will be obtained for the planimetry assessment at Visit 2 and submitted to Canfield Scientific, Inc. to determine the nail involvement. At all subsequent visits, appropriate photographic documentation of the same target toenail will be obtained and submitted to Canfield Scientific, Inc. to determine the nail involvement. Photographs of the target toenail will be collected using the procedures provided by Canfield Scientific, Inc. The photographs from each visit will be processed and reviewed by an independent panel. An image analysis will be conducted and numerical values for the % affected (in terms of surface affected for both the healthy and pathologic area of the target nail) will be reported. The % affected will be used to judge Satisfactory Clinical Cure.

9.6.14 Investigator Clinical Assessment:

An investigator will perform an exam of foot/toenail at each visit. Infected toenails will be counted and recorded. Nail appearance will be recorded.

9.6.15 Evaluation of Toenail Condition/Appearance:

The toenail, one of the two great toenails, that the investigator considers to be the most appropriate as the target toenail will be identified and designated as the "target toenail" at Visit 2 and used for evaluations.

The overall appearance of the target toenail over time will be monitored during the study:

1. Self-assessed by patients. The results of the self-assessment will be recorded by the patient before beginning therapy at Visit 2 and at all subsequent visits. Patients will use a 5-point scale (see Appendix A) for target toenail appearance.

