10.5 Efficacy Endpoints

The primary endpoint is the proportion of patients in each treatment group with a complete therapeutic cure of onychomycosis of the target toenail assessed at each of two test-of-cure visits (Day 141 and Day 365).

The secondary endpoint-1 is the proportion of patients in each treatment group with a complete or almost complete therapeutic cure of onychomycosis of the target toenail assessed at each of the two test-of-cure visits (Day 141 and Day 365).

The secondary endpoint-2 is the proportion of patients in each treatment group with a mycologic cure of the target toenail assessed at each of the two test-of-cure visits (Day 141 and Day 365).

A Randomized, Placebo-Controlled, Double-Blind, Parallel-Group, Multi-Site Phase 2b Clinical Study to Assess the Efficacy, Safety and Tolerability of 8-Week Regimens of Novexatin®, 10% Topical Solution (Taro Pharmaceuticals, USA, Inc.) in Patients with Mild to Moderate Onychomycosis

The secondary endpoint-3 is the proportion of patients in each treatment group with a complete clinical cure of the target toenail assessed at each of three test-of-cure visits (Day 141, Day 281 and Day 365).

The secondary endpoint-4 is the proportion of patients in each treatment group with a satisfactory clinical cure of the target toenail assessed at each of three test-of-cure visits (Day 141, Day 281 and Day 365).

Complete therapeutic cure is defined as both complete clinical and mycological cure of the target toenail

Almost complete therapeutic cure is defined as both mycological and satisfactory clinical cure of the target toenail

Mycological cure is defined as a negative KOH test **and** a negative fungal culture.

Complete clinical cure is defined as 0% nail involvement.

Satisfactory clinical cure is defined as $\leq 5\%$ of the target toenail involvement.

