### **Secondary Endpoints:**

1. The proportion of patients in each treatment group with a complete or almost complete therapeutic cure of onychomycosis of the target toenail assessed at each of the two test-of-cure visits (Day 141 and Day 365).
2. The proportion of patients in each treatment group with a mycological cure of the target toenail assessed at each of the two test-of-cure visits (Day 141 and Day 365).
3. The proportion of patients in each treatment group with a complete clinical cure of the target toenail assessed at each of three test-of-cure visits (Day 141, Day 281 and Day 365).
4. The proportion of patients in each treatment group with a satisfactory clinical cure of the target toenail assessed at each of three test-of-cure visits (Day 141, Day 281 and Day 365).

**Complete therapeutic cure** is defined as both complete clinical and mycological cure of the target toenail

**Almost complete therapeutic cure** is defined as both mycological and satisfactory clinical cure of the target toenail

**Mycological cure** is defined as a negative KOH test **and** a negative fungal culture.

**Complete clinical cure** is defined as 0% nail involvement.

**Satisfactory clinical cure** is defined as  $\leq 5\%$  of the target toenail involvement.

**NOVUM PHARMACEUTICAL RESEARCH SERVICES  
STATISTICAL ANALYSIS PLAN**

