#### **8.2.3 Additional Analyses**

In addition to the efficacy statistical analyses specified in the protocol, the analyses described in Section 8.2.1 above, including sensitivity analyses, will also be performed using the following endpoints:

1. Primary endpoint (complete therapeutic cure) with Canfield's evaluation for % toenail involvement.
2. Secondary endpoint #1 (complete or almost complete therapeutic cure) with Canfield's evaluation for % toenail involvement for complete cure in addition to the current evaluation for almost complete cure by Canfield's evaluation.
3. Secondary endpoint #3 (complete clinical cure) with Canfield's evaluation for % toenail involvement for complete cure.

Patients will only be included in analyses 1, 2 and 3 above if they meet inclusion criterion #6 (Mild to moderate severity at Visit 1 as defined by Investigator's estimation of approximately

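### Complete cure (0%) appears to be read by the investigator and satisfactory cure (5% or less) by planimetry, so secondary endpoint 1 combines two readers and endpoints 3 and 4 are not nested

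*Protocol*

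**What the plan says.** Protocol 9.6.13 plans two readings of percent involvement. In the first, "nail involvement of the target toenail over time will be monitored visually by an investigator at every visit". The second is image analysis of photographs by Canfield, with review by an independent panel, from Visit 2 onward. The section ties one endpoint component to the planimetry figure: "The % affected will be used to judge Satisfactory Clinical Cure".

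The definitions name no reader. Protocol 10.5 says "Complete clinical cure is defined as 0% nail involvement", and SAP section 6 repeats that it "is defined as 0% nail involvement". Satisfactory clinical cure is "≤ 5% of the target toenail involvement" (Protocol 9.1). The composite follows: "Almost complete therapeutic cure is defined as both mycological and satisfactory clinical cure of the target toenail". Secondary endpoint 1 counts patients "with a complete or almost complete therapeutic cure of onychomycosis of the target toenail". Endpoint 3 is complete clinical cure alone, and endpoint 4 is satisfactory clinical cure alone.

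SAP 8.2.3 adds Canfield-based versions of the primary endpoint and of secondary endpoints 1 and 3, beyond the protocol's analyses. For endpoint 1 it describes Canfield's evaluation "for complete cure in addition to the current evaluation for almost complete cure", and it gives Canfield as that current evaluation. These added analyses keep only patients whose involvement is 10-35% by Canfield.

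**The concern.** On paper the thresholds are nested: 0% lies inside 5% or less, so every complete cure should also be a satisfactory cure, and the endpoint 4 rate should be at least the endpoint 3 rate. If the two thresholds are read by different instruments, neither statement is guaranteed. A nail that the investigator reads as clear and planimetry reads as 6% succeeds on endpoint 3 and fails on endpoint 4. With negative mycology it also succeeds on the primary endpoint and on endpoint 1.

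Endpoints 1, 3 and 4 are each tested under the hierarchical scheme (SAP 8.2.1), and Protocol 10.6 says the efficacy results will size Phase 3. An easier endpoint with a lower rate than the harder one would be difficult to interpret, and endpoint 1 would describe no single reader's view of the nail.

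**Working it through.** **1. The plan's own figure.** Protocol 10.2 assumes therapeutic cure of 49% on active and 21% on placebo, with a two-sided 0.05 pooled Z test. With a mean rate of 0.35:

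n = [1.960 x sqrt(2 x 0.35 x 0.65) + 0.842 x sqrt(0.49 x 0.51 + 0.21 x 0.79)]^2 / 0.28^2 = 44.4, so 45 per group.

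The plan states 46, which gives 81.5% power. 46/(1 - 0.23) = 59.7, so 60 per group and 180 in total. The figure reproduces, and it does not depend on who reads the 5% threshold.

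**2. Who reads what.**

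- *5% or less:* planimetry, stated in Protocol 9.6.13.
- *0%:* no sentence says. Four things point to the investigator:
  - SAP 8.2.3 lists complete cure by Canfield as additional to the protocol's analyses, and treats Canfield as the existing reader only for almost complete cure.
  - The sensitivity listing shell for the primary endpoint has one column headed Per-Protocol Evaluation beside another headed Canfield Evaluation.
  - The shells have Canfield tables for the primary endpoint and for endpoints 1 and 3 but none for endpoint 4, which fits endpoint 4 already being planimetric.
  - The investigator's visual assessment is the only other reading of percent involvement.

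**3. What follows for each pair of readings.** All rows assume mycological cure.

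| Row | Investigator | Planimetry | Primary and endpoint 3 | Endpoint 4 | Endpoint 1 as planned | Endpoint 1, planimetry only | Endpoint 1, investigator only |
|---|---|---|---|---|---|---|---|
| a | 0% | 5% or less | yes | yes | yes | yes | yes |
| b | 0% | above 5% | yes | no | yes | no | yes |
| c | above 0 to 5% | 5% or less | no | yes | yes | yes | yes |
| d | above 0 to 5% | above 5% | no | no | no | no | yes |
| e | above 5% | 5% or less | no | yes | yes | yes | no |
| f | above 5% | above 5% | no | no | no | no | no |

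Row b is the complete but not satisfactory patient. Mycology plays no part in endpoints 3 and 4, so among all patients the endpoint 4 rate minus the endpoint 3 rate is (c + e) - b. It is negative when b exceeds c + e.

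**4. Illustration of row b.** Let q be the share of complete therapeutic cures that planimetry reads above 5%. The documents give no value, so 5-20% is assumed.

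| q | Active: 49 x q | Placebo: 21 x q | Active patients of 46 | Placebo patients of 46 |
|---|---|---|---|---|
| 5% | 2.5 points | 1.1 points | 1.1 | 0.5 |
| 10% | 4.9 points | 2.1 points | 2.3 | 1.0 |
| 20% | 9.8 points | 4.2 points | 4.5 | 1.9 |

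The 49% and 21% are therapeutic cure rates. The documents give no expected rate for clinical cure alone. Therapeutic cures are a subset of complete clinical cures, so on the same assumption the number of row b patients counted in endpoint 3 would be at least this large. This is the gross count of discordant patients, not the net gap between endpoints 3 and 4.

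**5. Direction for endpoint 1.** Against a planimetry-only version, the planned rule can only add patients (row b). With the same q in both arms, the absolute difference then grows by (0.49 - 0.21) x q = 0.28q: 1.4 points at 5% and 5.6 points at 20%. Against an investigator-only version, the planned rule gains row e and loses row d, so the sign is not determined.

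**The case against.** The strongest reply is that the investigator's role in complete cure is inferred and that single-reader results are already planned. The first part stands: no passage assigns the 0% reading, and the plainest defect is that no cure definition names its reader. The second part stands only in part. SAP 8.2.3 gives Canfield-only versions of endpoints 1 and 3, and the shells list both readings by patient. Those analyses also restrict the population to 10-35% involvement by Canfield, so a difference from the main result could come from the reader or from the population. The restriction also applies a Visit 1 criterion, whereas planimetry starts at Visit 2. No investigator-only version of endpoint 1 or 4 is planned.

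It is also fair to say that the reach is limited. The primary endpoint uses only the 0% threshold, and these are secondary endpoints in a Phase 2b trial.

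A reader might infer three stronger things that the documents do not support:

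- *Endpoint 4 itself mixes readers.* It does not. It is satisfactory clinical cure alone, and Protocol 9.6.13 gives that to planimetry.
- *Endpoint 1 is inflated.* That is true only by comparison with a planimetry-only version. Against an investigator-only version the planned rule could be the stricter one.
- *Reader disagreement blurs the treatment difference.* With equal q in both arms the difference grows against planimetry alone. Dilution would need a further assumption, such as equal absolute misreading in both arms.

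**Conclusion.** The point holds as an incoherence between definitions and readers. Protocol 9.6.13 assigns the 5% threshold to planimetry, and SAP 8.2.3 with the shells implies that the investigator reads 0%. On that reading endpoint 1 passes on either of two instruments, endpoints 3 and 4 use different readers, and complete cure no longer guarantees satisfactory cure. The size is unknown. The 2.5-9.8 points of an active group and 1.1-4.2 points of placebo rest on an assumed 5-20% disagreement and on the planned therapeutic cure rates. They show scale only and say nothing about bias in any comparison. The sample size and the primary endpoint are unaffected. The change is worth making because the affected endpoints are formally tested and the repair is cheap.

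**What to change.** 1. Name the reader in each cure definition in SAP section 6.
2. Within each analysis of endpoints 1, 3 and 4, apply one reader to both the 0% and the 5% thresholds.
3. Report the other reader, again for both thresholds, as a sensitivity analysis in the same full ITT population. For that analysis drop the Canfield version of inclusion criterion 6, or show the restricted result in addition.
4. Record the change in SAP 8.7.

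Which reader is main is the sponsor's choice, and each has a price. Using the investigator for the 5% threshold departs from Protocol 9.6.13. Using planimetry for 0% would put endpoints 1 and 3 on a different reader from the one implied for the primary endpoint.

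The cost is a declared SAP change and a few extra tables. Both readings are scheduled at Visits 4, 5 and 7. The investigator listing shell carries percent involvement at every visit, and the Visit 7 bands separate values up to 5% from 6-9%. No new data are needed, and neither the sample size nor the primary endpoint changes.

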9.6.16 KOH Stain

At screening, a sample from both big toenails can be collected for subjects with a bilateral infection of the big toenails. At subsequent applicable visits, a sample from the target toenail will be collected and a KOH stain performed using standardized methodologies that will be provided to the Investigators.

If at Visit 1 the result of the KOH stain is negative then no further assessments need be conducted on this patient as they will not be eligible for inclusion. If at Visit 1 the KOH stain test is positive then a sample for mycological culture must be obtained (see Section 9.6.14) to confirm the result.

At Visits 4 and 7, a sample for KOH and mycological culture should be obtained so that subsequent analysis of the correlation between KOH stain and mycological culture results can be performed.

9.6.17 Sample for Mycological Culture

If at Visit 1 the result of the KOH stain is negative then no sample for mycological testing should be taken from this patient as they will not be eligible for inclusion. If at Visit 1 the KOH stain test is positive then a sample for mycological culture should be obtained to confirm the result.

At subsequent visits when a sample is collected for KOH stain a sample for mycological culture must also be obtained irrelevant of the results of the KOH stain.

At screening, samples for the mycological culture will be collected from the big toenail that resulted in a positive KOH stain. At subsequent visits, samples for mycological culture will be collected from the target toenail using the procedures provided by the central laboratory. The sample will be processed and sent to a central microbiological testing laboratory. It is anticipated that it will take 14 to 30 days for the microbiological laboratory to provide the investigator with the results of the culture. Refer to Appendix B.

9.6.18 Application Site Reactions:

At each visit following randomization the Investigator will evaluate the patient for local application site reactions and question patient regarding symptoms experienced since the previous visit based on the scale provided in Appendix C. Application Site reactions (see Appendix C) will be documented in the Source and CRF.

Application site reactions will not be separately recorded as AEs since they are being captured at each visit for erythema, burning/stinging, erosion, edema, pain, itching or dryness unless the Investigator feels it is appropriate to do so.

A Randomized, Placebo-Controlled, Double-Blind, Parallel-Group, Multi-Site Phase 2b Clinical Study to Assess the Efficacy, Safety and Tolerability of 8-Week Regimens of Novexatin®, 10% Topical Solution (Taro Pharmaceuticals, USA, Inc.) in Patients with Mild to Moderate Onychomycosis

9.6.19 Health Status/Adverse Events

At each visit, starting at Day 1, patients will be questioned regarding any changes in their medical status since their previous visit. New medical conditions or the worsening in severity of any concurrent medical conditions reported at baseline, or since the previous visit will be reported as new adverse events.

9.7 Adverse Events

The patients will be monitored throughout the study for any Adverse Events. At each visit following screening, patients will be questioned regarding any changes in their medical status since their previous visit. Observed changes during the clinical assessments at each visit, should be reported as adverse events. Each patient will be observed for signs and symptoms of local irritation and documented appropriately.

AEs will be collected through both solicited and unsolicited means and subsequently coded in tabular form using the MedDRA (Version 19 or higher) Adverse Event Dictionary. The patients will be encouraged to report signs, symptoms, and any changes in health to the clinic staff. Severity of each AE will be determined by the staff based on observation and questioning of the patients. The Investigator will judge the relationship of the event to the study treatments.

9.7.1 Definitions

Adverse Event: Any untoward medical occurrence in a patient or clinical investigation patient administered a pharmaceutical product and which does not necessarily have a causal relationship with treatment. An AE can therefore be any unfavorable and unintended sign, symptom, or disease, temporally associated with the use of a medicinal (investigational) product, whether or not related to this product. This includes events not seen at baseline, or worsened even if present at baseline.

Unexpected Adverse Event: An adverse event where the nature or severity of is not consistent with the applicable product information (e.g., Investigator's Brochure for an unapproved investigational product or package insert/summary of product characteristics for an approved product).

Adverse Drug Reaction: All noxious and unintended responses to a medical product related to any dose should be considered adverse drug reactions. The response to a 'medical product' means that a causal relationship between a medicinal product and an adverse event is at least a reasonable possibility, i.e. the relationship cannot be ruled out.

Pregnancy: Female patients of childbearing potential must have been using and must agree to continue to use accepted methods of birth control, throughout the study. All female patients are considered to be of childbearing potential unless they are premenarchal, have been surgically sterilized or have been postmenopausal for at least 12 months. Abstinence is an accepted method of birth control. Alternatively, any of the following methods of birth control are acceptable: oral contraceptives, contraceptive patches/implants (e.g., Norplant®), Depo-Provera®, double barrier methods (e.g., condom plus diaphragm with spermicide) or IUD. Prior to study enrollment

A Randomized, Placebo-Controlled, Double-Blind, Parallel-Group, Multi-Site Phase 2b Clinical Study to Assess the Efficacy, Safety and Tolerability of 8-Week Regimens of Novexatin®, 10% Topical Solution (Taro Pharmaceuticals, USA, Inc.) in Patients with Mild to Moderate Onychomycosis

women of childbearing potential must be advised of the importance of avoiding pregnancy during study participation.

A negative result of a urine pregnancy test having a minimum sensitivity of at least 50 mIU/ml for hCG should be obtained, prior to study participation, at Visit 1. Pregnancy testing will also be performed at every study visit and the results of all pregnancy tests (positive or negative) will be documented.

If following initiation of study treatment, it is subsequently discovered that a study patient is pregnant or may have been pregnant at the time of Investigational Product exposure, the Investigational Product will be permanently discontinued. The Principal Investigator must immediately notify the Medical Monitor of this event.

Protocol-required procedures for study discontinuation and follow-up must be performed on the patient. Other appropriate pregnancy follow-up procedures should be considered if indicated. In addition, the Principal Investigator must report to the sponsor follow-up information regarding the course of the pregnancy, including perinatal and neonatal outcome. Infants should be followed for a minimum of eight weeks after birth.

9.7.2 Severity of Adverse Event

The severity of the adverse event will be graded by the Investigator using the following criteria as guidelines:

- MILD: Awareness of symptom but does not interfere with routine activities
- MODERATE: Discomfort sufficient to interfere with routine activities
- SEVERE: Impossible to perform routine activities

